3.4 FIGURE 1 – TRIAL PROFILE

STATISTICAL ANALYSIS PLAN FOR ALAQ STUDY

3.5 STUDY ASSESSMENTS
3.5.1 Demographics and other baseline characteristics

The baseline summaries will include the below variables (Table 1), stratified by group.

Table 1. Demographic and other baseline characteristics at the time of crossover

Characteristic	AL → AQ → AL+AQ	AQ → AL → AL+AQ
Age (years)		
Median (IQR)		
Sex: female n(%)		
Weight (kg)		
Median (IQR)		
Height (cm)		
Median (IQR)		
Body Mass Index (kg/m ²)		
Mean(sd)		
Haemoglobin (g/dL)		
Mean(sd)		
WBC (10 ³ /uL)		
Median (IQR)		
Platelet count (10 ³ /uL)		
Median (IQR)		
Neutrophil count (%)		
Median (IQR)		
ALT (U/L)		
Median (IQR)		
AST (U/L)		
Median (IQR)		
Creatinine (mg/dL)		
Median (IQR)		
XXXX		

3.5.2 Pharmacokinetic assessments

Individual pharmacokinetic parameters of artemether/dihydroartemisinin, lumefantrine/desbutyl-lumefantrine and amodiaquine/desethylamodiaquine will be calculated after each dose administration using a non-compartment approach.

Total exposure up to the last measured concentration (AUC_{LAST}) will be calculated using the linear trapezoidal method for ascending concentrations and the logarithmic trapezoidal method for descending concentrations. The terminal elimination half-life ($t_{1/2}$) will be estimated by the slope (λ_Z) of the best-fit log-linear regression of the observed concentrations in the terminal elimination phase. Drug exposure will be extrapolated from the last observed concentration to time infinity by C_{LAST}/λ_Z for each individual subject to compute total drug exposure (AUC_{∞}). Maximum concentration (C_{MAX}) and time to maximum concentration (T_{MAX}) will be taken directly from the observed data. Apparent oral elimination clearance (CL/F) and apparent volume of distribution (V/F) will be computed individually according to the equations below.

$$CL/F = \frac{Dose}{AUC_{\infty}} \quad V/F = \frac{t_{1/2} \times CL/F}{\ln 2}$$

The pharmacokinetic parameters will be summarised for each drug stratified by arm (i.e., when administered alone or in combination). Similarly, descriptive statistics will be summarised by arm. Ln-transformed pharmacokinetic exposure parameters (C_{MAX} , AUC_{LAST} and AUC_{∞}) will be evaluated to assess potential drug-drug interactions. No drug-drug interaction is assumed if the 90% confidence intervals of the ratio (combination/alone) of C_{MAX} , AUC_{LAST} and AUC_{∞} fall within 80% to 125% [10]. The 90% confidence intervals of the ratio (combination (COMB)/alone (ALONE)) will be calculated according to equation below.

$$Mean\ ratio\ (\%) = 100 \cdot e^{Parameter_{combination} - Parameter_{alone}}$$

where $Parameter_{combination}$ and $Parameter_{alone}$ are the least square mean of the natural logarithm of parameters derived for the combination and alone administration, respectively. The upper and lower boundary of the 90% confidence interval are calculated as follow:

$$90\% \ Confidence\ Interval = 100 \cdot e^{(Parameter_{combination} - Parameter_{alone}) \pm t_{0.95} \cdot SE_D}$$

STATISTICAL ANALYSIS PLAN FOR ALAQ STUDY

where $t_{0.95}$ is taken from the student-t distribution, SE_D is the standard error of the difference of the test and reference least squares means. The pharmacokinetic parameters of combination to alone administration will be summarised in Table 2 below.

Table 2. Pharmacokinetic parameters of {Drug name} when administered alone and in combination.

Parameter	{Drug name} alone	{Drug name} combination	{Metabolite name} alone	{Metabolite name} combination
	Median (range)	Median (range)	Median (range)	Median (range)
C_{MAX} (ng/mL)				
T_{MAX} (h)				
CL (L/h)				
V (L)				
$t_{1/2}$ (h)				
AUC_{LAST} (ng \times h/mL)				
AUC_{∞} (ng \times h/mL)				

Abbreviations: C_{MAX} , maximum (peak) plasma concentration; T_{MAX} , time to maximum concentration; CL , elimination clearance; V , volume of distribution; AUC_{LAST} , area under the plasma concentration-time curve from time zero to last measurable drug concentration; AUC_{∞} , AUC from time zero extrapolated to infinity.

Drug-drug interaction results will be summarised in Table 3 below.

Table 3 Drug-drug interactions of artemether-lumefantrine and amodiaquine when administered in combination.

Parameter	ARM comb./alone administration	DHA comb./alone administration	LF comb./alone administration	DLF comb./alone administration	AQ comb./alone administration	DEAQ comb./alone administration
	Mean (90% CI)	Mean (90% CI)	Mean (90% CI)	Mean (90% CI)	Mean (90% CI)	Mean (90% CI)
C_{MAX} (ng/mL)						
AUC_{LAST}						

STATISTICAL ANALYSIS PLAN FOR ALAQ STUDY

(ng×h/mL)						
AUC _∞ (ng×h/mL)						

Abbreviations: C_{MAX}, maximum (peak) plasma concentration; AUC_{LAST}, area under the plasma concentration-time curve from time zero to last measurable drug concentration; AUC_∞, AUC from time zero extrapolated to infinity; ARM, Artemether; DHA, Dihydroartemisinin; LF, Lumefantrine; DLF, Desbutyl-lumefantrine; AQ, Amodiaquine; DEAQ, desethylamodiaquine.

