6.1.2 Visit 2-4

16 healthy subjects who fulfill the eligibility criteria will be recruited and randomized to the study.

Procedures on each admission (Appendix 2):

Visit 2

Day -1 (admission)

- Physical Examination and symptoms questionnaire assessment
- Chemistry, Hematology, FBS and urinalysis assessment
- 24-hour urine for creatinine clearance test
- Genetic sample collection (Genetic sample can be collected at any of the subsequent days or visits, if it is missed today)
- Vital signs will be checked every 4 hours.
- ECG monitoring according to table 2
- Holter monitoring (~30 mins baseline recording)
- Urine pregnancy test (if applicable)

Day 0-3 (admission)

- Daily physical examination and symptoms questionnaire assessment
- Vital signs will be checked before and every 4 hours after first dose.
- ECG monitoring according to table 2
- Continuous Holter monitoring during admission.
- Pharmacokinetic samples will be collected according to table 2
- Study drug administration (Artemether-lumefantrine OR Amodiaquine) will be given according to table 1.
- 24-hour urine for creatinine clearance test (Day 2)
- Chemistry, Hematology, FBS and urinalysis assessment before discharge

Day 4 (+1) (follow up)

• Physical Examination, vital signs and symptoms questionnaire assessment

- Pharmacokinetic sample collection
- ECG

Day 7 (+/-2d) (follow up)

- Physical Examination, vital signs and symptoms questionnaire assessment
- Chemistry, Hematology and urinalysis assessment
- Pharmacokinetic sample collection
- ECG
- Holter monitoring (~ 30 mins)

Day 14 (+/-2d) (follow up)

- Physical Examination, vital signs and symptoms questionnaire assessment
- Chemistry, Hematology and urinalysis assessment
- Urine pregnancy test (if applicable)
- Pharmacokinetic sample collection
- ECG

Day 21 (+/-2d) (follow up)

- Physical Examination, vital signs and symptoms questionnaire assessment
- Chemistry, Hematology and urinalysis assessment
- ECG

Day 28 (+/-2d) (follow up)

- Physical Examination, vital signs and symptoms questionnaire assessment
- Chemistry, Hematology and urinalysis assessment
- Urine pregnancy test (if applicable)
- Pharmacokinetic sample collection
- ECG
- Holter monitoring (~ 30 mins)

Day 35 (+/-2d) (follow up) (for Amodiaquine only)

- Physical Examination, vital signs and symptoms questionnaire assessment
- Chemistry, Hematology and urinalysis assessment
- ECG

Day 42 (+/-2d) (follow up) (for Amodiaquine only)

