- Chemistry, Hematology and urinalysis assessment
- Urine pregnancy test (if applicable)
- Pharmacokinetic sample collection
- ECG

Visit 4

Day -1 (admission)

- Physical Examination and symptoms questionnaire assessment
- Chemistry, Hematology, FBS and urinalysis assessment
- 24-hour urine for creatinine clearance test
- Vital signs will be checked every 4 hours.
- ECG monitoring according to table 2
- Holter monitoring (~30 mins baseline recording)
- Urine pregnancy test (if applicable)

Day 0-3 (admission)

- Daily physical examination and symptoms questionnaire assessment
- Vital signs will be checked before and every 4 hours after first dose.
- ECG monitoring according to table 2
- Continuous Holter monitoring during admission.
- Pharmacokinetic samples will be collected according to table 2
- Study drug administration (Artemether-lumefantrine AND Amodiaquine) will be given according to table 1.
- 24-hour urine for creatinine clearance test (Day 2)
- Chemistry, Hematology, FBS and urinalysis assessment before discharge

Day 4 (+1) (follow up)

- Physical Examination, vital signs and symptoms questionnaire assessment
- Pharmacokinetic sample collection
- ECG

Day 7 (+/-2d) (follow up)

- Physical Examination, vital sign and symptoms questionnaire assessment
- Chemistry, Hematology and urinalysis assessment
- Pharmacokinetic sample collection
- ECG
- Holter monitoring (~ 30 mins)

Day 14 (+/-2d) (follow up)

- Physical Examination, vital signs and symptoms questionnaire assessment
- Chemistry, Hematology and urinalysis assessment
- Urine pregnancy test (if applicable)
- Pharmacokinetic sample collection
- ECG

Day 21 (+/-2d) (follow up)

- Physical Examination, vital signs and symptoms questionnaire assessment
- Chemistry, Hematology and urinalysis assessment
- ECG

Day 28 (+/-2d) (follow up)

- Physical Examination, vital signs and symptoms questionnaire assessment
- Chemistry, Hematology and urinalysis assessment
- Urine pregnancy test_(if applicable)
- Pharmacokinetic sample collection

- ECG
- Holter monitoring (~ 30 mins)

Day 35 (+/-2d) (follow up)

- Physical Examination, vital signs and symptoms questionnaire assessment
- Chemistry, Hematology and urinalysis assessment
- ECG

Day 42 (+/-2d) (follow up)

- Physical Examination, vital signs and symptoms questionnaire assessment
- Chemistry, Hematology and urinalysis assessment
- Urine pregnancy test (if applicable)
- Pharmacokinetic sample collection
- ECG

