6.4. Pharmacokinetics

Blood for pharmacokinetic assessments may be obtained by individual needle stick or IV

cannula. If a cannula is used for collection of the whole blood samples, the cannula will be inserted into an arm vein within sufficient time before dosing and may be kept patent using a dilute heparin solution as a flush. An initial volume of approximately 1.0 mL of blood will be collected and discarded prior to collection of each whole blood sample to ensure that the saline or heparin solution does not artificially dilute the samples. If PK samples are collected via individual needle sticks rather than through a cannula, then no extra blood needs to be collected and discarded prior to the collection of the sample.

Each blood sample will be labeled with subject's number, schedule date and time, collection date and time. The actual time of each blood sample will be recorded on the case report form (CRF).

Regimen	Blood sampling	ECG measurements
Regimen 1: Artemether- lumefantrine (AL) Dosing: 0h, 8h, 24 h, 36 h, 48 h, 60 h	 Day 0: Hr. 0 (pre-dose), 0.25, 0.5, 1, 2, 3, 4, 6, 8 (pre-dose), 10, 12, 14 Day 1: Hr. 24 (pre-dose), 26, 28, 30, 36 (pre-dose), 38, 40, 42 Day 2: Hr. 48 (pre-dose), 48.25, 48.5, 49, 50, 51, 52, 54, 56, 60 (pre-dose), 61, 62, 64, 66 Day 3: Hr. 72 Day 4, Day 7, Day 14, Day 28 	Day -1: Hr. 0, 1, 2, 4, 6, 8, 10, 12, 14 Day 0: Hr. 0 (pre-dose), 1, 2, 4, 6, 8 (pre-dose), 10, 12, 14 Day 1: Hr. 24 (pre-dose), 26, 28, 30, 36 (pre-dose), 38, 40, 42 Day 2: Hr. 48 (pre-dose), 49, 50, 52, 54, 60 (pre-dose), 61, 62, 64, 66 Day 3: Hr. 72 Day 4, Day 7, Day 14, Day 21, Day 28
Regimen 2: Amodiaquine (AQ) Dosing: 0h, 8h, 24 h, 36 h, 48 h, 60 h	Day 0: Hr. 0 (pre-dose), 0.25, 0.5, 1, 2, 3, 4, 6, 8 (pre-dose), 10, 12, 14 Day 1: Hr. 24 (pre-dose), 26, 28, 30, 36 (pre-dose), 38, 40, 42 Day 2: Hr. 48 (pre-dose), 48.25, 48.5, 49, 50, 51, 52, 54, 56, 60 (pre-dose), 61, 62, 64, 66 Day 3: Hr. 72 Day 4, Day 7, Day 14, Day 28, Day 42	Day -1: Hr. 0, 1, 2, 4, 6, 8, 10, 12, 14 Day 0: Hr. 0 (pre-dose), 1, 2, 4, 6, 8 (pre-dose), 10, 12, 14 Day 1: Hr. 24 (pre-dose), 26, 28, 30, 36 (pre-dose), 38, 40, 42 Day 2: Hr. 48 (pre-dose), 49, 50, 52, 54, 60 (pre-dose), 61, 62, 64, 66 Day 3: Hr. 72 Day 4, Day 7, Day 14, Day 21, Day 28, Day 35, Day 42

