Regimen 3: Artemether- lumefantrine + amodiaquine (AL+AQ)	Day 0: Hr. 0 (pre-dose), 0.25, 0.5, 1, 2, 3, 4, 6, 8 (pre-dose), 10, 12, 14 Day 1: Hr. 24 (pre-dose), 26, 28, 30, 36 (pre-dose), 38, 40, 42 Day 2: Hr. 48 (pre-dose), 48.25, 48.5,	Day -1 : Hr. 0, 1, 2, 4, 6, 8, 10, 12, 14 Day 0 : Hr. 0 (pre-dose), 1, 2, 4, 6, 8 (pre-dose), 10, 12, 14 Day 1 : Hr. 24 (pre-dose), 26, 28, 30, 36

Table 2 Pharmacokinetic collection schedule for each study regimens

Dosing: 0h, 8h, 24 h, 36 h, 48 h,	49, 50, 51, 52, 54, 56, 60 (pre-dose), 61, 62, 64, 66 Day 3 : Hr. 72	(pre-dose), 38, 40, 42 Day 2 : Hr. 48 (pre-dose), 49, 50, 52, 54, 60 (pre-dose), 61, 62, 64, 66	
60 h	Day 4, Day 7, Day 14, Day 28, Day 42	Day 3 : Hr. 72	
		Day 4, Day 7, Day 14, Day 21, Day 28, Day 35, Day 42	

The time-window for the visit on Day 4 is + 1 day and for the visits on Days 7 - 42 is + 2 or - 2 days

Total blood collection for pharmacokinetic analysis will be around 165 mL.

The total blood collections for both laboratory assessments and pharmacokinetic sampling on each visit was summarized in Appendix 4.

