6.4.1. Pharmacokinetic Samples (Plasma Matrix)

Blood samples (1 mL for regimen 1, 2 and 2 mL for regimen 3) will be collected into properly labeled 2 mL sodium heparin blood collection tubes at the study times shown in Table 2.

Sample Handling

Upon collection, blood samples will be centrifuged for 7 minutes at 2000g at 4°C. After centrifugation, the plasma of each sample will be transferred via pipette to a pre-labeled sample storage tube and stored upright until analyzed.

Sample Storage

Samples will be immediately frozen in the storage tubes in the upright position in a non-self-defrosting freezer at -70°C or lower.

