	Day 14 (+/-2d) (follow up) Clinical lab (Chemistry 5 mL and Hematology 2 mL) (Total 7 mL) Pharmacokinetic sample collection (1 mL)	7 mL	1 mL	
	Day 21 (+/-2d) (follow up) Clinical lab (Chemistry 5 mL and Hematology 2 mL) (Total 7 mL)	7 mL	0	
	Day 28 (+/-2d) (follow up) Clinical lab (Chemistry 5 mL and Hematology 2 mL) (Total 7 mL) Pharmacokinetic sample collection (1mL)	7 mL	1 mL	
	Day 35 (+/-2d) (follow up) (for Amodiaquine only) Clinical lab (Chemistry 5 mL and Hematology 2 mL) (Total 7 mL)	7 mL	0	
	Day 42 (+/-2d) (follow up) (for Amodiaquine only) Clinical lab (Chemistry 5 mL and Hematology 2 mL) (Total 7 mL) Pharmacokinetic sample collection (1 mL)	7 mL	1 mL	
Visit 4	Day-1 (admission) Clinical lab (Chemistry 5 mL, Hematology 2 mL, and FBS 2 mL) (Total 9 mL)	9 mL	0 mL	140 mL
	Day 0-3 (admission) Clinical lab (Chemistry 5 mL,	9 mL	70 mL	

visit	laboratory assessments	PK Sampling	Blood sampling
Hematology 2mL ,and FBS 2mL) (Total 9 mL)			
Pharmacokinetic sample collection at			
Day 0 : Hr. 0 (pre-dose), 0.25, 0.5, 1, 2, 3, 4, 6, 8 (pre-dose), 10, 12, 14			
Day 1 : Hr. 24 (pre-dose), 26, 28, 30, 36 (pre-dose), 38, 40, 42			
Day 2 : Hr. 48 (pre-dose), 48.25, 48.5, 49, 50, 51, 52, 54, 56, 60 (pre-dose), 61, 62, 64, 66			
Day 3 : Hr. 72			
Total 35 time-points (2 mL each time- points) (1 mL for Artemether -lumefantrine and 1 mL for Amodiaquine			
Day 4 (+1) (follow up)	0	2 mL	
Pharmacokinetic sample collection (2 mL)			
Day 7 (+/-2d) (follow up)	7 mL	2 mL	
Clinical lab (Chemistry 5 mL and Hematology 2mL) (Total 7 mL)			
Pharmacokinetic sample collection (2 mL)			
Day 14 (+/-2d) (follow up)	7 mL	2 mL	
Clinical lab (Chemistry 5 mL and Hematology 2 mL) (Total 7 mL)			
Pharmacokinetic sample collection (2 mL)			
Day 21 (+/-2d) (follow up)	7 mL	0	
Clinical lab (Chemistry 5 mL and Hematology 2mL) (Total 7 mL)			
Day 28 (+/-2d) (follow up)	7 mL	2 mL	
Clinical lab (Chemistry 5 mL and Hematology 2mL) (Total 7 mL)			
Pharmacokinetic sample collection (2 ml)			
Day 35 (+/-2d) (follow up)	7 mL	0	

visit		laboratory assessments	PK Sampling	Blood sampling
	Hematology 2mL) (Total 7 mL)			
	Day 42 (+/-2d) (follow up)	7 mL	2 mL	
	Clinical lab (Chemistry 5 mL and Hematology 2 mL) (Total 7 mL)			
	Pharmacokinetic sample collection (2 mL)			
Genetic sampling (10 mL)		10 mL		10 mL
Genetic sample can be collected at any schedule visits.				
	345 mL

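### Lumefantrine AUC-last is compared over unequal planned windows, Day 28 alone against Day 42 in combination, which can push the ratio slightly upward when there is no interaction

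*SAP*

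**What the plan says.** - **AL alone.** Protocol 6.4, Table 2, ends Regimen 1 sampling with "Day 3: Hr. 72 Day 4, Day 7, Day 14, Day 28". In Protocol 6.1.2, the last follow-up of Visits 2 and 3 is headed "Day 42 (+/-2d) (follow up) (for Amodiaquine only"), so AL alone has no Day 42 sample.
- **AL+AQ.** Table 2 ends Regimen 3 with "Day 4, Day 7, Day 14, Day 28, Day 42", and the Visit 4 heading "Day 42 (+/-2d) (follow up") carries no amodiaquine-only limit.
- **What is assayed.** Protocol 6.4.1 specifies "Blood samples (1 mL for regimen 1, 2 and 2 mL for regimen 3"). Appendix 4 explains the 2 mL as "1 mL for Artemether -lumefantrine and 1 mL for Amodiaquine", but only beside the inpatient times. The Day 42 row of Visit 4 is also 2 mL.
- **Visit windows.** The tolerance "for the visits on Days 7 - 42 is + 2 or - 2 days".
- **Analysis.** SAP 3.5.2 computes AUC-last as "Total exposure up to the last measured concentration", and its Table 2 footnote runs it to the last measurable concentration. Neither document sets a common end time or excludes a Day 42 lumefantrine result.
- **Role.** AUC-infinity, AUC-last and Cmax of each drug and metabolite are all primary (Protocol 3.1, SAP 2.2). No interaction is concluded if the 90% CIs of the ratios lie within 80% to 125% (Protocol 12, SAP 3.5.2).

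**The concern.** AUC-last to the last measurable concentration is a fair comparison when both periods are sampled over the same span. For lumefantrine the combination period may run 14 days longer by design. Any quantifiable concentration at Day 42 adds area to the numerator that could not have been collected for the denominator. The error has one direction, so averaging over subjects does not remove it. A reader of SAP Table 3 could take it for a small exposure increase caused by amodiaquine.

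Desbutyl-lumefantrine has the same schedule, but the documents give no half-life for it, so its effect cannot be sized. Artemether and DHA are not affected, nor is Cmax. Amodiaquine and desethylamodiaquine are sampled to Day 42 both alone and in combination.

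**Working it through.** **1. The plan's own figures confirm the schedule.** Appendix 4 blood volumes, with 12 + 8 + 14 + 1 = 35 inpatient PK times:

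- AL alone: 9 + 9 + 4×7 + 1×(35 + 4) = 85 mL (stated 85), which is PK to Day 28.
- AQ alone: 9 + 9 + 6×7 + 1×(35 + 5) = 100 mL (stated 100), PK to Day 42.
- AL+AQ: 9 + 9 + 6×7 + 2×(35 + 5) = 140 mL (stated 140), PK to Day 42.
- Total: 10 + 85 + 100 + 140 + 10 = 345 mL (stated 345).

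**2. Hand check of the ratio with no interaction.** For one-phase decline with half-life h days and a single dose at day s, the ratio is about [1 − 2^(−(42−s)/h)] / [1 − 2^(−(28−s)/h)]. The six doses run from 0 to 60 h, so s = 0 and s = 2.5 bracket the answer:

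- h = 3: 1.0015 to 1.0027
- h = 4.5: 1.0120 to 1.0178
- h = 6: 1.0329 to 1.0445

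**3. Full calculation.** Inputs from the documents: half-life 3 to 6 days (Protocol 1), doses at 0, 8, 24, 36, 48 and 60 h, Table 2 sampling times, linear-up/log-down trapezoid (SAP 3.5.2). Assumptions: first-order absorption with single-dose Tmax 7 h (the Protocol gives about 6 to 8 h). The two-phase profile assumes amplitudes of 85% at a 24 h half-life and 15% terminal. The same profile is used in both periods.

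| Half-life | Ratio, one-phase | Ratio, two-phase | Day 42 as % of Cmax, one-phase | Two-phase |
|---|---|---|---|---|
| 3 d | 1.0021 | 1.0007 | 0.01 | 0.003 |
| 4.5 d | 1.0148 | 1.0064 | 0.24 | 0.06 |
| 6 d | 1.0386 | 1.0191 | 1.07 | 0.28 |

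The last two columns are also the level below which the LLOQ must lie for the effect to occur. With the ±2-day windows at 6 days, the ratio ranges from 1.026 to 1.054 (one-phase) and from 1.013 to 1.026 (two-phase). A different absorption model (2 h lag, ka 0.5/h) gave 1.002, 1.015 and 1.039, with an AUC-infinity ratio of 1.000.

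**4. Effect on the decision.** The documents give no CV. With 16 subjects and CV 20%, the within-subject SD on the log scale is √ln(1.04) = 0.198, and the SE of the log ratio is 0.198 × √(2/16) = 0.070. The chance that AUC-infinity and AUC-last both pass was simulated (15 df, true ratio 1, the two log ratios fully correlated, AUC-last shifted by the log of the ratio in step 3):

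| Case | One-phase | Two-phase |
|---|---|---|
| CV 20%, no artefact | 83.7% | 83.7% |
| CV 20%, 3 d, all 16 quantifiable | 83.3% | 83.5% |
| CV 20%, 4.5 d, all 16 | 80.2% | 82.2% |
| CV 20%, 6 d, all 16 | 72.8% | 79.0% |
| CV 20%, 6 d, half the subjects | 78.9% | 81.5% |
| CV 15%, no artefact | 98.3% | 98.3% |
| CV 15%, 6 d, all 16 | 94.7% | 97.1% |

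At a true ratio of 0.80 the joint pass stays at 5.0%.

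**5. Check of the remedy.** With no interaction, the Day 28 rule set out below gave ratios of 0.99996 to 1.00004 over 75 visit-window combinations per profile.

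**The case against.** **The effect may not exist.** It needs Day 42 lumefantrine to be assayed, which is inferred from the 2 mL volume, and to be quantifiable, with no LLOQ given. At a 4.5-day half-life the LLOQ must be below 0.24% of Cmax (one-phase) or 0.06% (two-phase). If Day 42 is unquantifiable, AUC-last ends by Day 28 in both periods. This stands and limits the weight of the point, but it does not argue against fixing the rule before data are seen: the rule then costs nothing.

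**It is small and conservative.** At CV 20% the shift is 0.09 to 0.21 SE at 4.5 days and 0.27 to 0.54 SE at 6 days. It cannot carry a ratio outside 80% to 125% alone, and AUC-infinity is a co-primary safeguard. All of this stands.

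**The pass rates omit Cmax.** This also stands. Adding Cmax (assumed CV 20%, correlation 0.5, ratio 1) lowers the baseline to about 72%, with 69% to 71% at 4.5 days and 63% (one-phase) or 68% (two-phase) at 6 days. The largest loss is then about 9 points instead of 11.

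**The remedy is not better in every case.** If the half-life truly rises from 4.5 to 6 days (AUC-infinity ratio 1.33), the Day 28 rule gives 1.29 and the current definition 1.34. If it falls from 6 to 4.5 days (AUC-infinity ratio 0.75) with an LLOQ of 2% of Cmax, both give 0.674. The rule removes the artefact of the planned windows; it does not repair every weakness of AUC-last.

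**Conclusion.** The concern holds. The planned windows differ by 14 days and the SAP does not align them. If Day 42 lumefantrine is assayed and quantifiable, the primary AUC-last ratio is biased upward by about 0.1% to 4% over the Protocol's half-life range, or up to 5.4% in the worst visit-window case. The bias does not produce a false conclusion of no interaction. It distorts one reported primary ratio and lowers the chance of a correct conclusion: by 1.5 to 3.5 points at 4.5 days and 4.7 to 10.9 points at 6 days, at an assumed CV of 20% with all 16 subjects quantifiable. The figures rest on assumed profile shapes and CVs and on an unknown LLOQ, so confidence in the size is moderate. Confidence in the direction is high. This is worth correcting because it is cheap, not because it threatens the trial.

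**What to change.** Add to SAP 3.5.2:

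> For lumefantrine and desbutyl-lumefantrine, the primary AUC-last ratio uses concentrations up to and including the Day 28 visit in both periods. If both Day 28 visit samples are quantifiable but were drawn at different actual times, the later profile is interpolated log-linearly to the earlier actual time. A period that becomes unquantifiable before Day 28 keeps its own last quantifiable time and does not shorten the other period. AUC-last including Day 42 is a sensitivity analysis, and Day 42 data are kept for λz, half-life and AUC-infinity.

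The cost is SAP wording and code; sampling and visits do not change. There are two downsides. A real change confined to the time after Day 28 will show only in AUC-infinity and the sensitivity analysis. Windows will still differ if one period becomes unquantifiable before Day 28, as with conventional AUC-last.

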Amodiaguine by oral administration is absorbed rapidly, and then extensively metabolized to N-desethylamodiaquine (active metabolite) and 2-hydroxy-desethyl-amodiaquine by hepatic first-pass effect. C_{max} of amodiaguine in plasma, whole blood and packed cells is 32±3ng/ml, 60±10ng/ml and 42±6ng/ml respectively; Tmax of amodiaguine is 0.5±0.03h, 0.5±0.1h and $0.5\pm0.1h$ respectively; AUC₀₋₈ of amodiaguine in plasma, whole blood and packed cells is 99 ± 19 ng·ml⁻¹h, 148 ± 25 mJ⁻¹h and 167 ± 72 ng·ml⁻¹h respectively. Cmax of desethylamodiaguine in plasma, whole blood and packed cells is 181±26ng/ml (19 fold higher than those of the parent drug), 561±70ng/ml and 561±143ng/ml respectively; Tmax for desethylamodiaguine is 3.4±0.8h, 2.2±0.5h and 3.6±1.1h respectively; and AUC0-24 for desethylamodiaquine in plasma, whole blood and packed cells is 2304±37ng·ml⁻¹h, 6811±752ng·ml⁻¹h and 5713±1269ng·ml⁻¹h respectively (whole blood AUC was higher than plasma AUC, P<0.001). The trial of ¹⁴C-labelled amodiaquine administered orally to Wistar rats showed that amodiaquine can be distributed widely in body with the main organs of accumulation being kidney, liver, bone marrow and spleen. Amodiaquine is not observed in plasma 8 hours after administration, whereas the concentration of desethylamodiaquine in plasma at 96h is 29 ± 8 ml⁻¹. The half-life of amodiaguine in plasma is 5.2 ± 1.7 h, and elimination half-life ($\beta_{t1/2}$) of desethylamodiaquine in plasma is 9-31 days. The bioavailability of amodiaquine is decreased due to first-pass hepatic metabolism. The plasma protein binding rate of amodiaguine and desethylamodiaguine is greater than 90%. The T_{max} of amodiaguine taken orally by patients with falciparum malaria is 1.75h, distinctly longer than the T_{max} of healthy volunteers (18).

Potential interactions through hepatic metabolism

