All study drugs are metabolized in the liver. Artemether and lumefantrine are primarily metabolized via CYP3A4 (19). Artemether metabolism through CYP3A4 produces an active metabolite, dihydroartemisinin (DHA) that contributes substantially to its antimalarial activity. Artemether is also a CYP3A4 inducer, while lumefantrine inhibits CYP2D6 (20). The clearance of amodiaquine and metabolism to its main metabolite, N-desethylamodiaquine, is catalyzed primarily by CYP2C8 (21). As some of these drugs share the same enzymes or have effects on the enzymes for other drug metabolism, the co-administration may result in clinically significant drug-drug interactions that can cause unanticipated adverse reactions or therapeutic failures. To evaluate whether such effects take place, we propose to co-administer these drugs in this healthy volunteer study.

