2.4 SECONDARY ENDPOINTS

- a. Elimination clearance (CL/F), terminal elimination half-life (t_{1/2}) and apparent volume of distribution (V_d) of artemether, lumefantrine and amodiaquine and their metabolites when given alone and in combination.
- b. Safety and tolerability parameters, including adverse events, electrocardiographic changes, vital signs and biochemical assessments. •
- c. Pharmacogenetic polymorphisms in the case of unusual metabolizeStudy design

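### Half-life and V/F, named secondary endpoints, get no combination/alone ratio or interval, and the lumefantrine terminal slope may be fitted over different days in the two regimens

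*SAP*

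**What the plan says.** Protocol 3.2 and SAP 2.4 name CL/F, terminal half-life and volume of distribution as secondary endpoints, "of artemether, lumefantrine and amodiaquine and their metabolites when given alone and in combination".

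SAP 3.5.2 sets out two kinds of output:

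- **Comparative.** The ln-transformed Cmax, AUClast and AUC∞ "will be evaluated to assess potential drug-drug interactions", through a ratio of least-squares means with a 90% CI judged against 80–125%. SAP Table 3 has rows for these three parameters only, with a column for each of six analytes.
- **Descriptive.** "The pharmacokinetic parameters will be summarised for each drug stratified by arm (i.e., when administered alone or in combination"). "The pharmacokinetic parameters of combination to alone administration will be summarised in Table 2 below", and that table gives a median and range in separate alone and combination columns. Half-life, V, CL and Tmax appear only here; Cmax and AUC appear here as well.

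Protocol 12.5.1 is also descriptive for these parameters: means with SD or 95% CI, or medians with range, and no ratio.

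Under Protocol section 4, all 16 subjects receive each drug alone and then the combination. Protocol Table 2 ends PK sampling at Day 28 for artemether-lumefantrine alone and at Day 42 for the combination. SAP 3.5.2 takes the half-life from the best-fit log-linear regression of the terminal phase and does not fix which samples enter it.

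**The concern.** The protocol's rationale for the study is shared or altered drug-metabolising enzymes: "To evaluate whether such effects take place, we propose to co-administer these drugs in this healthy volunteer study". Half-life is the planned parameter that bears most directly on elimination, yet a reader of the planned tables would see two medians with two ranges. There would be no estimate of the change and no measure of its uncertainty. The ranges reflect differences between subjects, which a paired comparison removes, and the protocol indicates that these are wide: the half-life "of desethylamodiaquine in plasma is 9-31 days", and that of lumefantrine is 3 to 6 days.

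The unequal lumefantrine sampling adds a second problem. If a later phase is slower, a slope that includes Day 42 in one regimen and stops at Day 28 in the other can produce a half-life difference with no interaction behind it.

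At stake is the interpretation of the secondary PK endpoints. The primary no-interaction decision is not affected.

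**Working it through.** **1. Which parameters lack a comparison.** SAP 3.5.2 defines CL/F = Dose/AUC∞ and V/F = t½ × CL/F / ln 2, per subject. With the same dose in both regimens:

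- ln(CL/F ratio) = −ln(AUC∞ ratio). The CL/F ratio and its 90% CI are obtained by inverting the AUC∞ result. For example, a simulated AUC∞ ratio of 1.412 (1.272 to 1.569) gives CL/F 1/1.412 = 0.708 (1/1.569 to 1/1.272, i.e. about 0.64 to 0.79).
- ln(V/F ratio) = ln(t½ ratio) − ln(AUC∞ ratio). Once the t½ ratio is known the V/F point estimate follows, and only its interval is new.

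Appendix 3 has a single artemether-lumefantrine dose for subjects of 35 kg or more, so the dose cancels. For amodiaquine it cancels unless a subject changes weight band between admissions. Of the three named parameters, half-life is therefore the one independent quantity with no comparison.

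**2. Precision lost by comparing medians (desethylamodiaquine half-life).** Inputs:

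- n = 16 (Protocol section 4).
- Between-subject log SD = ln(31/9)/4 = 0.309. This reads 9–31 days as ±2 SD between subjects, which is an assumption.
- Within-subject log SD 0.15, range 0.10 to 0.25. This is also an assumption; the documents give no figure.

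The SD of the paired mean log ratio is s_w × √(2/16), or 0.15 × 0.354 = 0.053. The SD of the log ratio of the two medians, from 40,000 simulated trials, is 0.086. The variance ratio is (0.086/0.053)² ≈ 2.6, and about 3.4 to 2.0 as s_w runs from 0.10 to 0.25.

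| Situation | Ratio of medians, 90% of trials | Paired analysis |
|---|---|---|
| No true change, s_w 0.15 | 0.87 to 1.15 | 90% CI about ×/÷ exp(1.753 × 0.053) = 1.10 |
| Half-life truly 20% longer, s_w 0.15 | 1.04 to 1.38 | 90% CI excludes 1 in 95% of trials (99.9% to 63% for s_w 0.10 to 0.25) |

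With no true change, the ratio of medians reaches 1.20 or more in about 2% of trials (0.3% to 7% over the range).

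**3. Sampling window.** The last dose is at 60 h, or Day 2.5. For lumefantrine, Day 28 is 25.5 days later, which is 25.5/6 = 4.25 to 25.5/3 = 8.5 half-lives. Day 42 is 39.5 days later, or 6.6 to 13.2 half-lives. Whether Day 42 enters the fit depends on assay sensitivity, which the documents do not give, so the window may differ by regimen and by subject. For desethylamodiaquine, 39.5 days is 39.5/9 = 4.4 to 39.5/31 = 1.3 half-lives. At the long end the slope is poorly determined, and the assumed s_w would have to absorb that error.

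**4. Metabolite/parent AUC.** The point estimate of its change is the quotient of adjacent columns of SAP Table 3. The interval is not recoverable from that table, because it depends on the within-subject correlation of parent and metabolite. As an illustration, assume a shared within-subject SD of 0.30 and 0.15 for each analyte alone. The 90% CI is then ×/÷ exp(1.753 × √(0.30² + 0.15²) × √2/4) = 1.23 for an AUC ratio, against ×/÷ exp(1.753 × √(2 × 0.15²) × √2/4) = 1.14 for the metabolite/parent ratio. These two factors follow entirely from the assumed inputs.

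**The case against.** A reader might infer that the trial cannot tell whether an exposure change comes from elimination or absorption, and so fails at what it set out to test. The documents do not support that. The objectives are to characterise interactions and PK properties, and no objective asks for that separation. Individual parameters are computed for every subject, so a paired half-life ratio can be obtained from the planned data; it is simply not prespecified. Nor would the extra ratios settle the mechanism. CL/F and V/F both contain bioavailability, and the protocol says that first-pass hepatic metabolism lowers amodiaquine bioavailability, so altered metabolism could move bioavailability and the metabolite/parent ratio together.

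A reader might also infer that the plan uses pairing for Cmax and AUC and withholds it elsewhere. Neither document says so. Protocol section 12 speaks of ANOVA comparisons across groups, and SAP 3.5.2 names no subject, period or sequence term.

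Two further points stand against overstating the loss. Chance alone seldom produces a 1.20 ratio of medians under the base assumptions. And the variance figures rest on assumed SDs and on a 9–31 day range whose source population and distribution are not given.

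What remains is that two named secondary endpoints have no planned estimate of change, the stated summary is less precise than one available from the same data, and the lumefantrine slope has no common window.

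**Conclusion.** The point holds as a minor improvement. The planned tables contain no estimate or interval for the change in half-life, and none for V/F, although each subject provides both values. CL/F needs nothing new. The precision gain from pairing, about 2 to 3.4 times lower variance than a ratio of medians for desethylamodiaquine half-life, depends on the two assumptions in step 2 of the working. It would shrink if estimation error in the terminal slope pushed the within-subject SD above 0.25. The lumefantrine window mismatch is plain from Protocol Table 2, but its effect on the fitted half-life cannot be sized from the documents.

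**What to change.** In SAP 3.5.2, add rows to SAP Table 3, each a subject-level ln combination/alone ratio with a 90% CI:

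- t½ for all six analytes, and V/F for the three parent drugs;
- metabolite/parent AUC for dihydroartemisinin/artemether, desbutyl-lumefantrine/lumefantrine and desethylamodiaquine/amodiaquine.

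Write the paired form out in full, since the existing equation names no subject term. For these half-life comparisons, fit λz over the same nominal sampling days in both regimens, to Day 28 for lumefantrine and desbutyl-lumefantrine. State that the AUC∞ extrapolation used in the primary rule stays as specified. No CL/F row is needed; a note that its ratio is the reciprocal of the AUC∞ ratio at equal dose is enough.

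Label the new rows as supportive estimates, not further 80–125% tests, and say that they do not conclusively separate absorption from elimination.

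The cost is a few lines of SAP text and some table rows. No samples or assays are added, and the primary decision rule does not change.
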